To determine the usefulness, feasibility and efficacy of the E-scale system coupled with a standardized behavioral treatment weight-loss intervention for overweight or obese wheelchair users.

1.2 Specific Aims: List the goals of the proposed study (e.g., describe the relevant hypotheses or the specific problems or issues that will be addressed by the study).

Aim 1. To investigate the usefulness and feasibility of the E-scale system and efficacy of the E-scale coupled with a weight-loss intervention to assist overweight or obese wheelchair users with losing weight.

Hypothesis 1a: The E-scale will be useful based on self-reported feedback from wheelchair users by more than 50% stating that the E-scale is easy to use, their preferred weight monitoring system, them feeling that they would use the E-scale if it was available for them to purchase.

Hypothesis 2b: The E-scale will be feasible by providing accurate (+/- 2 lbs. from a calibrated scale measurement) and repeatable (<3lbs difference from day-to-day) weight measurements and by the wheelchair users continuing to use the scale more than 70% of the days of the study.

Hypothesis 2c: The E-scale coupled with the weight loss intervention will demonstrate efficacy by wheelchair users having significant improvements in weight, abdominal girth, body fat percentage and score on the Self-Rated Abilities for Health Practices Scale (SRAHP).

1.3 Background: Briefly describe previous findings or observations that provide the background leading to this proposal.

Wheelchair users have about twice the prevalence of obesity than the general population. There is also very little or no technology to which they have access to measure their weight frequently in their homes. Research however, has shown that monitoring your body weight frequently (i.e. daily) yields significantly better weight loss and weight maintenance results. This research has never included wheelchair users because they have not had access to technology to be able to measure their weight daily. The E-scale was developed as a weight monitoring technology for wheelchair users and has been tested for precision and accuracy in the laboratory.

1.4 Significance: Why is it important that this research be conducted? What gaps in existing information or knowledge is this research intended to fill?

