During the next 12 weeks, subjects will be asked to weigh themselves every day with the E-scale app and record their diet, exercise and weight every day with the LoseIt! app. The data that is reported in the LoseIt! app by the subjects will be monitored by the study team using the ascendapp for LoseIt!, which allows a "coach" to monitor all of the data submitted by a client. The weight loss curriculum involves weekly lessons for the participants to learn and practice things like counting calories and fat, reorganizing their kitchens, doing more cardio work around the house, etc. This curriculum was adapted from the Diabetes Prevention Program Group Lifestyle Balance (DPP GLB) curriculum at Pitt specifically for people with mobility impairments. The study team will send periodic emails with comments to the participants encouraging their progress and adherence to the protocol and lesson materials for that week. Every week at a pre-defined time, a group chat room will be conducted with all of the subject's and the research team invited to attend to go over the lesson for that week and to have a group discussion for the participants to share successes and difficulties with the group. The chat room will be hosted using Adobe Connect with the audio and video capabilities disabled. The link to the chat room for each week will be emailed to the subjects along with the lesson materials. The curriculum disbursement, progress emails, and chat rooms will be led by a dietitian/nutritionist with experience in leading group weight loss programs.

During the last week of the study (week 13). The subjects will be asked to come back to the lab in-person where their weight will again be measured using the roll-on scale. Their

abdominal girth and body-fat percentage will also be measured again. The SRAHP will be administered to the subjects again and they will also be given the final questionnaire, System Usability Scale (SUS), which will evaluate how they felt about the E-scale and some aspects of entire study. Any android devices that were loaned to the subjects during the study will be collected and the apps on their personal devices will be deleted if they wish. Over the next few days, the study team will visit all of the subject's homes to remove the E-scales or the participants can bring them with them to the lab.

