[\[reviewer notes→\]](#)

2.12 **Does this research study involve any type of planned deception?**

If Yes, you are required to request an alteration of the informed consent process (question 4.7)

* No

[\[reviewer notes→\]](#)

2.13 **Does this research study involve the use of UPMC/Pitt protected health information that will be de-identified by an IRB approved "honest broker" system?**

* No

[\[reviewer notes→\]](#)

2.14

Will protected health information from a UPMC/Pitt HIPAA covered entity be accessed for research purposes or will research data be placed in the UPMC/Pitt medical record?

* No

2.14.1

Will protected health information from a non-UPMC/Pitt HIPAA covered entity be obtained for research purposes or will research data be placed in the non-UPMC/Pitt medical record?

* No

[\[reviewer notes→\]](#)

2.15

Does this research study involve the long-term storage (banking) of biological specimens?

* No

[\[reviewer notes→\]](#)

2.16

Will research participants be asked to provide information about their family members or acquaintances?

* No

[\[reviewer notes→\]](#)

2.17

What are the main outcome variables that will be evaluated in this study?

Subjective feedback from the survey about the usefulness and participants' satisfaction with portions of the program and E-scale.

Accuracy and repeatability of the E-scale measurements

Weight change, abdominal girth change, body-fat percentage change and Self-Rated Abilities for Health Practices (SRAHP) change

2.18

Describe the statistical approaches that will be used to analyze the study data.

* Addressed below:

Since there is only one group, most outcome variables will be analyzed using summary statistics. Baseline and final measurements will also be analyzed using paired t-tests.

[\[reviewer notes→\]](#)

2.19

Will this research be conducted in (a) a foreign country and/or (b) at a site (e.g., Navajo Nation) where the cultural background of the subject population differs

substantially from that of Pittsburgh and its surrounding communities?

- * No

Note that copies of training records, licenses, certificates should be maintained in the study regulatory binder and are subject to audit by the Research Conduct and Compliance Office (RCCO).

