Transfers for weighing: During the process of measuring the participant's height and weight, we will have them transfer to a mat table independently or with assistance. During the transfers, we will have a spotter for all transfers and will provide someone who has been trained to assist with transfers help if needed.

Using apps and adobe connect: During the study we will have the participants using the LoseIt! app, the E-scale app and adobe connect. LoseIt! and E-scale apps will be installed on their android device or one will be provided to them to use during the study. Non-personal logins for these devices will be provided to them so that no identifiable information is ever communicated with these apps. Adobe connect will be used to conduct weekly chat sessions with no audio or video being used. We will email the participants a link to join the chat room and ask them to join using their first names only.

5.2

What steps will be taken in the event that a clinically significant, unexpected disease or condition is identified during the conduct of the study?

* Not Applicable

5.3

All the risk questions (screening, intervention/interaction, follow-up) have been merged into one question (5.1).

[\[reviewer notes→\]](#)

5.4

Do any of the research procedures pose a physical or clinically significant psychological risk to women who are or may be pregnant or to a fetus?

* No

[\[reviewer notes→\]](#)

5.5

Do any of the research procedures pose a potential risk of causing genetic mutations that could lead to birth defects?

* No

[\[reviewer notes→\]](#)

5.6

Are there any alternative procedures or courses of treatment which may be of

benefit to the subject if they choose not to participate in this study?

* No

If **Yes**, describe in detail:

[\[reviewer notes→\]](#)

5.7

Describe the specific endpoints (e.g., adverse reactions/events, failure to demonstrate effectiveness, disease progression) or other circumstances (e.g., subject's failure to follow study procedures) that will result in discontinuing a subject's participation?

* Describe below:

If the subject is admitted to the hospital for more than 5 days we will remove them from the study. Also if the subject has not participated in any study procedures for 2 weeks they will be removed from the study.

[\[reviewer notes→\]](#)

5.8

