*** Upload Data Security Form:**

Name Modified Date
Data Security Assessment form 10/10/2017 11:04 AM

Address what precautions will be used to maintain the confidentiality of the research data collected in paper format if applicable:

Records will be coded by assigning a case number unique to this study. The linkage code will be stored electronically and not with other paper based files. All electronic data will be stored on the University of Pittsburgh network. Paper based records will be kept in a locked file room within the Human Engineering Research Laboratories. Access to both the electronic and paper based files is restricted to the Principal Investigator and the associated research staff working on the project.

5.15.1

Does your research study require a data security review? Answer Yes if any of the following conditions are met:

- Identifiable or *coded data will be collected, stored, or transmitted using any of the following technologies: mobile app, web-based site or survey, wearable device, text messaging, electronic audio, photographic, or video recording or conferencing **and/or**
- The IRB requested a data security review during their review of the study

* Yes

***Coded:** Identifying information (such as name) that would enable the investigator to readily ascertain the identity of the individual to whom the private information or specimens pertain has been replaced with a code (number, letter, symbol, or any combination) and a key to decipher the code exists, enabling linkage of the identifying information to the private information or specimens

5.16

If the subject withdraws from the study, describe what, if anything, will happen to the subject's research data or biological specimens.

If the subject withdraws from the study, any existing data will be rendered anonymous and included in results. We will ask the participant to answer the final questionnaire if they are willing to. Because this is a usefulness, feasibility and efficacy trial, even partial data could provide us with useful results.

5.17

Following the required data retention period, describe the procedures utilized to protect subject confidentiality. (e.g., destruction of research records; removal of identifiers; destruction of linkage code information; secured long-term retention)

Following the data retention period, the linkage code file will be deleted. Data will be retained for a longer term using the security measures already outlined in section 5.15.

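### Final efficacy values are planned only at the week-13 lab visit, so the paired t-tests describe the people who attend it, not everyone who started

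*Combined protocol and SAP*

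**What the plan says.** - **Objective.** Hypothesis 2c in section 1.2 states that the E-scale with the programme "will demonstrate efficacy by wheelchair users having significant improvements in weight, abdominal girth, body fat percentage" and in the SRAHP score. The abstract (CS2.1) names efficacy at 13 weeks among the primary outcomes.
- **Analysis.** Section 2.18 plans summary statistics for most outcomes and adds: "Baseline and final measurements will also be analyzed using paired t-tests". It gives no analysis population and no rule for missing values.
- **Collection of final values.** In section 2.6, during week 13, "subjects will be asked to come back to the lab in-person where their weight will again be measured using the roll-on scale". At the same visit "abdominal girth and body-fat percentage will also be measured again. The SRAHP will be administered to the subjects again". The paragraph then lists the final questionnaire separately and identifies it as the System Usability Scale.
- **Removal.** Section 5.7 removes a person after a hospital stay of more than 5 days, and also "if the subject has not participated in any study procedures for 2 weeks they will be removed from the study". It mentions no exit measurement.
- **Withdrawal.** Section 5.16 says that "any existing data will be rendered anonymous and included in results. We will ask the participant to answer the final questionnaire", if willing, on the ground that "even partial data could provide us with useful results".
- **Follow-up.** Section 2.7 answers No to follow-up procedures for research purposes.

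**The concern.** A paired t-test needs a baseline and a final value from the same person. The plan collects the final value at one visit and asks leavers only for a usability questionnaire. The efficacy estimate will therefore rest on attendees, while 5.16 gives the impression that leavers are represented. One of the two removal rules acts on non-participation, so attendees and leavers may differ in how much they changed.

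What is at stake is the estimated change and the group it describes. With at most 15 people, each missing final value is at least 1/15 of the starters. A week-13 value that was never taken cannot be recovered by later analysis, so this has to be settled before people leave.

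**Working it through.** **Step 1: trace each outcome to a final value.** The plan has no figure to reproduce, since section 3.12 says no sample size calculation was done. The check starts from the text.

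| Outcome | Final value for attendees (2.6) | Final value requested from leavers (5.16, 5.7, 2.7) |
|---|---|---|
| Weight | Week-13 lab, roll-on scale | None |
| Abdominal girth | Week-13 lab | None |
| Body fat | Week-13 lab | None |
| SRAHP | Week-13 lab | None; the final questionnaire is a different instrument |

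With k leavers among 15 starters, the paired t-test uses 15 − k pairs. A leaver's existing data can enter the summary statistics, but they contain no week-13 value.

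**Step 2: how far the two means could differ.** The maximum of 15 starters comes from CS2.1 and 3.11. Everything else is assumed, because the documents give no dropout rate, effect or SD. Let completers lose 6 lb on average and k leavers lose L lb.

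- Completers' mean = 6
- All-starter mean = [(15 − k) × 6 + k × L] / 15
- Bias = difference = (k/15) × (6 − L)

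| k | L (lb) | All-starter mean (lb) | Bias (lb) |
|---|---|---|---|
| 0 | any | 6.00 | 0 |
| 2 | 2 | 82/15 = 5.47 | 0.53 |
| 2 | 0 | 78/15 = 5.20 | 0.80 |
| 5 | 2 | 70/15 = 4.67 | 1.33 |
| 5 | 0 | 60/15 = 4.00 | 2.00 |
| 5 | 6 | 90/15 = 6.00 | 0 |
| 5 | 8 | 100/15 = 6.67 | −0.67 |

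**Step 3: compare with sampling error.** At an assumed SD of 8 lb, the completers' 95% half-width is t(0.975, n − 1) × 8/√n.

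- n = 10: 2.262 × 8/√10 = 5.72 lb. The 2.00 lb bias is 2.00/5.72 = 0.35 of it.
- n = 13: 2.179 × 8/√13 = 4.83 lb. The 0.80 lb bias is 0.80/4.83 = 0.17 of it.

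**Step 4: what inviting leavers would recover.** If r leavers attend and resemble the rest, the available-pairs mean is [(15 − k) × 6 + r × L] / (15 − k + r).

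- k = 5, L = 0: with r = 2 the mean is 60/12 = 5.00, and the bias falls from 2.00 to 1.00. With r = 3 it is 60/13 = 4.62, and the bias is 0.62.
- k = 2, L = 2: with r = 1 the mean is 80/14 = 5.71, and the bias falls from 0.53 to 0.25.

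If the more engaged leavers are the ones who attend, less is recovered. Suppose that of 5 leavers, 2 attend and lost 2 lb, and 3 stay away and lost 0. The all-starter mean is 64/15 = 4.27, so the bias without the invitation is 1.73. With it the mean is 64/12 = 5.33, and the bias is still 1.07.

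**The case against.** - **Leavers are already included under 5.16.** Their existing data are. But existing data hold no final value, and 2.18 gives no route for partial data into the t-tests.
- **The final questionnaire may be something else.** Section 2.8 lists an uploaded Final Survey, and the supporting documents list the System Usability Scale separately; the survey's content is not visible. This leaves a little room for doubt about SRAHP, although SRAHP has its own upload and 2.6 lists it apart. It leaves none for weight, girth or body fat, which no questionnaire can supply.
- **Daily weights fill the gap.** E-scale and LoseIt! weights cover weight only, up to the time of leaving. The E-scale is itself under evaluation and is installed after baseline, and the plan does not name these readings as a substitute.
- **The fix may recover little.** This stands in part. People with two weeks of complete non-participation are the least likely to make a lab visit.
- **This is a small, exploratory, single-group study.** That stands and limits the severity. Hypothesis 2c nevertheless sets significant improvement as its test of efficacy.

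A reader might also infer four stronger things that the documents do not support:

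- **The reported weight loss will be inflated.** Step 2 shows positive, zero and negative bias, and nothing in the documents selects among them.
- **Nothing at all is planned for people removed under 5.7.** The documents do not say whether removal is handled as withdrawal under 5.16. If it is, their data are kept and the questionnaire requested. On either reading, no final efficacy measurement is planned.
- **Anonymisation makes pairing impossible.** Section 5.16 gives no timing, and 5.17 deletes the linkage file only after the retention period. Pairing fails only if the link is cut at withdrawal.
- **The significance result would change.** With 10 completers, mean 6 lb and SD 8 lb, p = 0.042. Adding 5 leavers at zero change gives a mean of 4.00 lb and p = 0.045. In this illustration the estimate moves and the test hardly does.

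**Conclusion.** The point holds in limited form. As written, all four efficacy outcomes receive a final value only at the week-13 visit, none is requested from leavers, and the paired t-tests therefore describe attendees. This follows from the text and needs no assumption, except that for SRAHP it relies on 2.6's identification of the final questionnaire.

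Whether the estimate is biased, by how much and in which direction cannot be established. The 0.5 to 2.0 lb range depends on the assumed dropout and on leavers losing less than completers. Even its upper end is about a third of the completers' confidence half-width at the assumed SD. I rate it a cheap improvement, minor to should-fix; what raises it above wording is that the missing values cannot be obtained afterwards.

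**What to change.** 1. **Collection.** In 5.16, and for people removed under 5.7, invite those who are willing to the week-13 weight, girth, body-fat and SRAHP measurements already planned, as well as the questionnaire. Leave the removal rules as they are. State whether 5.16 covers people removed under 5.7. State that a leaver's data are anonymised only after this visit, so that final values can be paired with baseline through the existing study code. Bring the answer in 2.7 into line.
2. **Analysis.** In 2.18, run the paired t-tests on all starters with both values, including leavers who attend. Label the result as available pairs, and report the number of and reasons for missing final values.
3. **Optional sensitivity results.** Missing change set to zero could be shown as a point estimate only, because its interval is artificially narrow (width 11.45 lb falls to 7.81 lb in the five-leaver example). A mixed model on the E-scale weights is possible for weight alone, subject to the limits noted above. It also assumes that a leaver's later course is predictable from the weights recorded before leaving.

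**Cost.** A small IRB modification to 5.16, 5.7 and possibly 2.7 and the consent wording (the consent pages were not available for this review); keeping the linkage for leavers until week 13; and one extra request to each. No new procedure is added, and week 13 lies within the participation period in 2.11. Those who attend face the risk of falling during transfers already listed in 5.1; this deserves explicit mention for people removed after a hospital stay, and suitability is for the investigator and the IRB to judge. Some will decline, so recovery will be incomplete, and the estimate may become less favourable.

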3.1 What is the age range of the subject population?

18-80

3.2 What is their gender?

* Both males and females

Provide a justification if single gender selected:

3.3 Will any racial or ethnic subgroups be explicitly excluded from participation?

* No

If **Yes**, identify subgroups and provide a justification:

3.4 For studies conducted in the U.S., do you expect that all subjects will be able to comprehend English?

* Yes

[\[reviewer notes\]](#)

3.5 Participation of Children: Will children less than 18 years of age be studied?

* No

If **No**, provide a justification for excluding children:

Since we are investigating weight changes or weight loss, we do not want to include children who may be growing.

[\[reviewer notes\]](#)

3.6 Does this research study involve prisoners, or is it anticipated that the research study may involve prisoners?

* No

[\[reviewer notes\]](#)

3.7 Will pregnant women be knowingly and purposely included in this research study?

* No

[\[reviewer notes\]](#)

3.8 Does this research study involve neonates of uncertain viability or nonviable neonates?

- * No

[\[reviewer notes→\]](#)

3.9 Fetal Tissues: Does this research involve the use of fetal tissues or organs?

- * No

[\[reviewer notes→\]](#)

--->

3.10 What is the total number of subjects to be studied at this site, including subjects to be screened for eligibility?

Note: The number below is calculated by summing the data entered in question 3.11. Any additions or changes to the values entered in 3.11 will be reflected in 3.10.

- * 20

3.11

Identify each of the disease or condition specific subgroups (include healthy volunteers, if applicable) that will be studied.

Click on the "Add" button and specify for each subgroup:

- 1) how many subjects will undergo research related procedures at this site; and**
- 2) if applicable, how many subjects will be required to undergo screening procedures (e.g., blood work, EKG, x-rays, etc.) to establish eligibility. Do Not include subjects who will undergo preliminary telephone screening.**

*

Subgroup	Number to undergo research procedures	Number to undergo screening procedures
All subjects	15	20

3.12 Provide a statistical justification for the total number of subjects to be enrolled into this research study at the multicenter sites or this site.

- * Described below:

Since this is an efficacy and exploratory study no sample size calculation was needed or conducted. Similar weight loss studies include 10-20 people in each group session or cohort.

[\[reviewer notes→\]](#)

3.13 Inclusion Criteria: List the specific criteria for inclusion of potential subjects.

- Use Wheelchair as primary means of mobility
- Uses a bed with 4 legs
- BMI ≥ 27 and ≤ 40.0
- age 18-80
- Has daily access to Internet to access LoseIt website and/or app and weekly chat meeting (Adobe Connect)
- Currently owns or willing to use an android device
- Provides physician's clearance to participate in a weight loss intervention
- Speaks English

3.14 Exclusion Criteria: List the specific criteria for exclusion of potential subjects from participation.

- Presence of an unstable condition requiring physician-supervised diet and exercise (e.g., diabetes, recent myocardial infarction)
- Presence of condition precluding engagement in exercise at moderate intensity (e.g., asthma, congestive heart failure, etc.)
- Pregnancy or intention to become pregnant during study
- Currently being treated for any psychological issues or problems, taking any psychotropic medications, or receiving treatment with psychotropic medications within the previous 6 months
- Reported alcohol intake > 4 drinks/day
- Reported participation in a formal weight loss program, loss of $\geq 5\%$ weight in the past 6 months, or current use of weight loss medication.
- History of bariatric surgery (lap-band, gastric bypass, etc.)
- Planned extended vacations, absences, or relocation during study
- A score ≥ 20 on the Center for Epidemiologic Studies Depression Scale (CES-D)
- A classification of Anorexia Nervosa, Bulimia Nervosa or Binge Eating Disorder on the Eating Disorder Diagnosis Scale (EDDS)
- Unwilling to provide a diary of 3 days diet prior to beginning the intervention

3.15 Will HIV serostatus be evaluated specifically for the purpose of participation in this research study?

* No

If Yes, provide a justification:

[\[reviewer notes→\]](#)

- 4.1** Select all recruitment methods to be used to identify potential subjects:
- Advertisements
 - Research Registry
 - Pitt + Me
 - Other Strategies: Described below

Advertisements

Upload the advertisements for review:

Name	Modified Date
PRO16110460 [name].pdf	10/10/2017 10:29 AM
Flyer	4/18/2017 3:45 PM

Research Registry

List the IRB approval number and title for each registry source:

- Human Engineering Research Laboratories (Pitt IRB #PRO12080311)
- Department of Physical Medicine and Rehabilitation (Pitt IRB #PRO12030122)

4.2

Provide a detailed description of your recruitment methods, including identifying and initiating contact with participants:

We will distribute and post flyers at locations where wheelchair users meet (i.e., doctors offices, support groups, adaptive sporting events, etc.). We will also send flyers to wheelchair users in two wheelchair research registries and through the CTSI registry. We will also utilize social media to spread the word about the study and the Pitt+me registry. This would include posts with our flyer, a link to the Pitt+me study page, etc.

Note: Questions jump from 4.2 to 4.6 as questions 4.3-4.5 have been removed and the information is now captured in 4.1

[\[reviewer notes→\]](#)

- 4.6** **Are you requesting a waiver to document informed consent for any or all participants, for any or all procedures? (e.g., a verbal or computerized consent script will be used, but the subjects will not be required to sign a written informed**

consent document. *This is not a waiver to obtain consent.*

* Yes

4.6.1

Identify the specific research procedures and/or the specific subject populations for which you are requesting a waiver of the requirement to obtain a signed consent form.

Addressed below:

If not all, identify the specific procedures and/or subject populations for which you are requesting a waiver:

The only activities that will be conducted before obtaining written consent is a phone or in-person screening to determine that the potential participant meets most of the eligibility criteria prior to having them travel to our lab.

4.6.2

Indicate which of the following regulatory criteria is applicable to your request for a waiver of the requirement to obtain a signed consent form.

45 CFR 46.117(c)(2)

45 CFR 46.117(c)(1) That the only record linking the subject and the research would be the consent document and the principal risk would be potential harm resulting from a breach of confidentiality. Each subject will be asked whether the subject wants documentation linking the subject with the research, and the subject's wishes will govern; or

45 CFR 46.117(c)(2) That the research presents no more than minimal risk of harm to subjects and involves no procedures for which written consent is normally required outside of the research context.

4.6.2.1

Address why the specific research procedures for which you are requesting a waiver of the requirement to obtain a signed consent form present no more than minimal risk of harm to the research subjects:

We will go through a series of questions over the phone that determine if a person meets some of the criteria. The least personal and invasive questions that are similar to everyday conversations will be asked, followed by questions similar to those asked when making a clinical appointment. Questions will be discontinued and no information will be maintained if the person is ineligible for any criteria.

4.6.2.2

Justify why the research listed in 4.6.1 involves no procedures for which written informed consent is normally required outside of the research context:

The screening will only involve questions that occur during normal conversation and making a clinical appointment, and no identifiable information will be recording with the screening unless they complete the screening and are willing to participate.

4.6.3

Address the procedures that will be used and the information that will be provided (i.e., script) in obtaining and documenting the subjects' verbal informed consent for study participation:

When a potential subject responds to the ads, a member of the research team will go through the attached phone or in person screening script. The participant will be asked if it

is okay that we go through a series of questions to determine if they are eligible for the study, and instructed that they may discontinue and choose not to answer at any time. As soon as an answer to a screening question makes them ineligible, no information about them will be saved and the screening discontinued. If they meet the screening eligibility requirements, they will be invited to come to the lab and their screening answers will be kept on the secured server in our department.

Upload Scripts:

Name Modified Date
[Screening.docx](#) 6/24/2017 3:07 PM

[reviewer notes→]

4.7 Are you requesting a waiver to obtain informed consent or an alteration of the informed consent process for any of the following?

* No

4.7.1 If Yes, select the reason(s) for your request:

There are no items to display

General Requirements: The Federal Policy **[45 CFR 46.116 (d)]** specifies in order for a waiver of consent to be approved, the request must meet four criteria. For each request, you will be asked to provide a justification addressing how each of these criterion is met.

[reviewer notes→]

4.8

Are you requesting an exception to the requirement to obtain informed consent for research involving the evaluation of an 'emergency' procedure?

Note: This exception allows research on life-threatening conditions for which available

treatments are unproven or unsatisfactory and where it is not possible to obtain informed consent.

* No

[\[reviewer notes\]](#)

4.9

Upload all consent documents for watermarking:

Draft Consent Forms for editing:

Name Modified Date

ICF 10/19/2017 3:33 PM

Approved Consent Form(s):

Name Modified Date

ICF 12/13/2017 11:35 AM

[\[reviewer notes\]](#)

4.10

Will all potential adult subjects be capable of providing direct consent for study participation?

*

Yes

[\[reviewer notes\]](#)

4.11

At what point will you obtain the informed consent of potential research subjects or their authorized representative?

After performing certain of the screening procedures, but prior to performing any of the research interventions/interactions

4.11.1

Address why you feel that it is acceptable to defer obtaining written informed consent until after the screening procedures have been performed.

The questionnaire portion of the screening procedures will be done over the phone or in person prior to the subject coming to the lab so that the subjects will not have to make a trip to the lab location if they will not be eligible. Once the subject is at the lab in person, informed consent will be obtained before their weight and height are measured and they are asked to complete the Center for Epidemiologic Studies Depression Scale (CES-D) and the Eating Disorder Diagnosis Scale (EDDS).

4.11.2

Taking into account the nature of the study and subject population, indicate how the research team will ensure that subjects have sufficient time to decide whether to participate in this study. In addition, describe the steps that will be taken to

minimize the possibility of coercion or undue influence.

The study will be described to the potential subjects over the phone or in person prior to them coming to the lab. Once they come to the lab, informed consent will be obtained where they will be given time to decide if they want to proceed with the study.

[reviewer notes]

4.12 Describe the process that you will employ to ensure the subjects are fully informed about this research study.

* Addressed below:

This description must include the following elements:

- who from the research team will be involved in the consent process (both the discussion and documentation);
- person who will provide consent or permission;
- information communicated; and
- any waiting period between informing the prospective participant about the study and obtaining consent

In addition, address the following if applicable based on your subject population:

- process for child assent and parental permission
 - continued participation if a child subject turns 18 during participation
- process for obtaining proxy consent and assent for decisionally impaired subjects
 - continued participation if subject regains capacity to consent

All members of the research team will be involved with discussing and obtaining informed consent at the beginning of the subject's initial visit. The information about the study will be described during the screening and again when the potential subject comes into the lab, and all questions answered. This will give the subjects adequate time to decide to participate or not. The subjects will provide their own consent.

4.13 Are you requesting an exception to either IRB policy related to the informed consent process?

- For studies involving a drug, device or surgical procedures, a licensed physician who is a listed investigator is required to obtain the written informed consent unless an exception to this policy has been approved by the IRB
- For all other studies, a listed investigator is required to obtain consent (Note: In order to request an exception to this policy, the study must be minimal risk)

* No

If Yes, provide a justification and describe the qualifications of the individual who will obtain consent:

4.14 Will you inform research subjects about the outcome of this research study following its completion?

* No

If Yes, describe the process to inform subjects of the results:

[\[reviewer notes\]](#)

5.1

Describe potential risks (physical, psychological, social, legal, economic or other) associated with screening procedures, research interventions/interactions, and follow-up/monitoring procedures performed specifically for this study:

*

View	
Research Activity: Consent, measurements and questionnaires
 
Common Risks: No Value Entered
 
Infrequent Risks: breach of privacy and confidentiality
 
Other Risks: No Value Entered

View	
Research Activity: Installation and removal of escale
 
Common Risks: No Value Entered
 
Infrequent Risks: damage to bed or surrounding areas
 
Other Risks: No Value Entered

View	
Research Activity: Transfers for weighing
 
Common Risks: No Value Entered
 
Infrequent Risks: Falling during transfers
 
Other Risks: No Value Entered

View	
Research Activity: Using apps and adobe connect
 
Common Risks: No Value Entered
 
Infrequent Risks: breach of privacy and confidentiality
 
Other Risks: No Value Entered

View	
Research Activity: Using E-scale
 
Common Risks: No Value Entered
 
Infrequent Risks: Breach of privacy with motion being detected. Height of the bed is increased by approximately 1/2 inch which could make transfers more difficult.
 
Other Risks: No Value Entered

5.1.1 **Describe the steps that will be taken to prevent or to minimize the severity of the potential risks:**

Consent, measurements and questionnaires: During all activities of consent, measurements and questionnaires we will provide the subjects will a private location to answer the questions. Subject codes will be used on all data collection forms. All identifiable information will be stored in a locked file room separate from the research data. The only linkage code will be stored on a password protected department server.

Installation and removal of E-scale: The study team will visit the participants' homes to install and remove the E-scale. It is possible that during this time, damage could be caused

to the participant's bed or surrounding areas. The investigator is liable for any damage that occur as a result of participation in the study and damage will be reimbursed accordingly. During the first visit, the investigator will assess the condition of the bed and items placed near the bedside. After such verification, it is to the discretion of the investigator if he wishes to continue with installation of E-Scale or disqualify the participant due to concerns with the bed. IRB # PRO14080007 is a past study using these scales with no adverse events.

Use of E-scale: During the use of the E-scale, the bed height will be raised by approximately 1/2 in when the sensors are under the bed legs. This may make transfers to and from bed more difficult for the wheelchair users. We will describe this risk during the consent process so they are aware and can withdraw from the study if they feel it will be an issue. The E-scale also collects the weight from the bed legs continuously and as such changes in weight distribution may make it possible to detect when the person is in or out of bed and if they are moving. We will also make the participants aware of this risk during the consent process.

